Appendix I

Example patient documentation handout – see separate document for complete form with header/footer

Easy Stretch Toolkit

Who placed the tools? Circle one: patient/caregiver

Tool (size and color): _____ Placement location*: _____

*See attached picture.

Date	AM – Number of minutes used	PM – Number of minutes used

Appendix J – Cranial Nerve Assessment form - see separate document for complete form with header/footer

Easy Stretch Toolkit
Cranial Nerve Assessment: Oral Motor / Facial Measurements

Nerve	Task	Comments	Initial Exam Pass/Fail	Final Exam Pass/Fail
CN I Olfactory	Smell orange peel			
CN III Oculomotor	Follow the finger			
CN IV Trochlear	"H"			
CN V Trigeminal	Ophthalmic – brush across forehead			
	Maxillary – cheekbone			
	Mandibular- chin			

[name] and [name]

[figure not shown]
Version 10/October 2020

Page 18 of 24

	Corneal Reflex Test			
	Masseter /Temporalis–clench teeth			
	Jaw Jerk			
CN VII Facial	Crease forehead			
	Close eyes			
	Close eyes against resistance			
	Puff out cheeks			
	Smile and show teeth			
CN IX Glossopharyngeal	Gag reflex			
CN X Vagus	Say "ah"			
CN XI Accessory	Sternocleidomastoid and traps –			
	Head turn against resistance			
	Shoulder shrug - resistance			
CN XII Hypoglossal	Motor to muscles – Stick out tongue			

Week #: 1 Completed on ____ / ____ / ____ Time: _____ By: _____
 Week #: 12 Completed on ____ / ____ / ____ Time: _____ By: _____

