The Toolkit is not currently available to the general population and the current project will be the first time this product has been studied. We, the investigators and the creators posit that the Easy Stretch Toolkit will be applicable for neonate, pediatric and adult burn victims. This trial will include the adult and pediatric burn population. If this clinical trial is successful, our goal would be to expand to children under the age of 7, including the neonate population and ultimately to market, mass produce and sell the product to all patient populations, including patients with acute burn injuries. We would plan to conduct a larger trial (with a power analysis after we determine effect sizes) to further investigate efficacy of the Easy Stretch Toolkit. The need for early intervention in facial scar management was documented by Parry et. al. and Clayton et. al. [1,6]. In the future, another focus would be on the early use of these devices as a method for both preserving and increasing range of motion and elasticity in patients immediately following a burn injury. Additional target populations include patients with lip contractures following cleft lip surgery, as well as research into use of the Toolkit as an oral stimulation device for use in the NICU population. Use of the Easy Stretch Toolkit with each of these populations will need to be researched and studied by the creators; we plan to submit amendments to this parent protocol to include additional patient populations and indications in the future.

3. Concise Summary of Project:

Our proposed study and design is intended to study two Aims:

- 1) To determine whether use of the devices results in measurable change in range of motion and quality of life via pre- and post-use data and measurements for orofacial movements and function.
- 2) To develop an effective prescriptive rehabilitative plan for orofacial scar management for the patient to follow including an 8 week active treatment period.

Experimental Device:

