healing phase, ie., there are no concerns for injury to new or healing skin or wound dehiscence. A 20 subject sample size can generate meaningful estimates for the change and its variation, and within the range that sample size is recommended for feasibility study based the consideration in gain of precision for each increase of 1 in sample size [13]. Participants will need to be able to complete the entire 2 month prescriptive program. All participants will need to be able to attend weekly visits via in person or electronic means (telehealth) such as Skype, Zoom or other electronic platform for an enrollment screening, followed by a total of 8 weeks of treatment. Pediatric participants will need consent from a caregiver who will commit to being present for all in person or electronic visits as well. Participants who are referred to the study will be contacted via phone to determine eligibility criteria. If the participant meets eligibility requirements and selects telehealth option, a copy of the written consent form will be emailed to the participant. Verbal consent will then be obtained for enrollment in the study and background information will be obtained for the case history form. A package will be mailed to the participant including a full set of tools, a pupil distance eye ruler, copy of the consent form, written subject handouts including pages for weekly documentation of use of the tools, and return envelopes for homework and tools. If the subject lives locally and wishes to be seen at a UTMB clinic or their place of residence, visits may be done in person as well. Telehealth option is available for all study participants, ages 7 and up.

In cases of verbal consent, the investigators will request verbal confirmation by the subject/parent that they signed and dated the written consent form. If unable to print the consent/assent/permission, the subject/parent will sign and date a blank piece of paper with a written statement that they voluntarily agree to participate in the protocol. This statement will include the protocol number and name (Easy Stretch Toolkit, #18-0005). After signing and dating the newly created document, the study participant or legally authorized representative will send a photograph of the signed and dated statement or consent form by fax, text message or email to the investigator/designee or may return the document by mail at a later date. In all cases, informed consent will be obtained prior to participation in the trial.

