for 60 minutes (+/- 10 minutes) 2 times per day for each day of the study. Frequency of use of the device will be closely documented by the Speech Pathologists and the patient or caregiver using the provided charting system (Appendix I). Because use of the devices will be prescriptive, the applicable head shape(s) and placement(s) will vary by individual and by week. Specifically, placement(s) is (are) expected to vary each week based on the clinical needs of the subject and outcomes seen from the prior week's intervention. For monitoring purposes, data will be gathered at the initial assessment and 1 time per week thereafter (+/- 2 days) for the duration of the 8 week trial. As a result, data will be evaluated as to the prescriptive plan for deficits for specific facial landmarks and their associated muscle groups (cheeks, nasolabial folds, upper lip, mentolabial junction and modiolus). Subject safety will be met via an initial training session and weekly one-on-one follow-up visits via FaceTime, Skype or in person visit with the monitoring Speech Pathologist to assure appropriate use of the devices. Patient (or parent) handouts (Appendix I) will be provided to assist with recording of time spent using the devices and with which tool and placement location.

Assessment of the patient after completion of informed consent

- Photograph of the patient's face from the front, as well as their side profile (weekly), with measurements taken from the photograph at specific points. At this time, profile photographs will not be used for measurements or analysis but will be kept to show visual changes over time.
- Oral-motor facial examination will be conducted.

Targeted muscle groups [8]

The facial muscles to be targeted include:

- Levator labii superioris – elevates the upper lip and deepens nasolabial furrow
- Buccinator – controls movement of the cheeks and assists in sucking in neonates and mastication in pediatrics and adults
- Depressor anguli oris – assists with frowning, pulls corner of mouth inferiorly
- Mentalis – protrudes lower lip, inward and upward movement of the soft tissue of the chin
- Zygomaticus major – pulls angle of mouth upward and laterally
- Zygomaticus minor – raises upper lip
- Nasalis – compresses bridge, depresses tip of nose, elevates corners of nostrils
- Levator anguli oris – assists with smiling, elevates angle of the mouth
- Depressor septi – depression of the nasal septum

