The primary outcome will be change in degree of facial movement during different facial expressions as described above pre- and post-study. The secondary outcome will be any improvements in quality of life pre- and post-study as captured by the Facial Disability Index. The Facial Disability Index will be used as a validated quality of life instrument [12]. See Appendix M. Although it is somewhat dated (1996) and it was intended for use with facial neuromuscular disorders and facial palsy, its questions were deemed the most relevant for this study after thorough review of available burn, facial palsy and general quality of life measures.

The subjects will not be responsible for any research-related costs; insurance companies will not be billed. Validated parking will be offered if attending visits in person.

5. Sub-Study Procedures:

Not applicable.

6. Criteria for Inclusion of Subjects:

We plan to recruit 20 adult or pediatric patients who have sustained facial burns or who have sustained a facial injury resulting in scarring, tightness, limited range of motion of facial skin or musculature or fibrosis and are in the chronic phase of recovery to complete the 8 week treatment.

1. Age 7-80
2. Male or Female Sex
3. Patients who have sustained a facial burn and are now in the chronic phase, or any patient experiencing facial tightness or limited range of motion due to other problems, including patients s/p radiation to the head and neck, trauma, scarring and scleroderma
4. Chief complaint(s) of limited mouth opening, difficulty chewing or speaking, decreased range of motion for oral structures, and/or limited facial expressions
5. Subject or caregiver (parent or guardian, in case of pediatric population) must be able to give informed consent
6. Subject or caregiver (parent or guardian, in case of pediatric population) must be able to perform exercises at home and must be able to record time spent using the devices.
7. Participants who are undergoing other treatment methods such as use of compression garments, skin grafting, radiation or other facial surgery, etc must suspend all of these treatments for the duration of the 2 month trial.
8. Internet access including access to FaceTime, Skype or Zoom and email access if electing telehealth option for enrollment

7. Criteria for Exclusion of Subjects:

The following will exclude patients from participation in the study:

[name] and [name]

Version 10/October 2020

Page 9 of 24

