1. planned or unplanned surgeries for facial skin grafting around lips or nose or oral commissure release during the upcoming 8 weeks
2. completion of any massaging or other stretching exercises or programs not specified by the creators
3. use of new creams or topical treatments for the duration of enrollment in the study.
4. acutely burn-injured patients
5. incarceration, or pregnancy

9. Sources of Research Material:

We are collecting clinical and demographic data from the electronic charts. We are also collecting data as shown in Appendix H, I, J, K, L. These will be obtained via photographs of the subject during different facial expressions which are uploaded into a software program for measurements to be taken.

9. Recruitment Methods and Consenting Process:

The investigators will request a HIPPA Waiver to identify potential subjects. Potential subjects may be patients or former patients of the investigators. Additionally, they may be identified via clinic lists or outside referral sources. The potential subjects will be identified / referred by any clinician or physician and their patient(s) will be sent a recruitment letter or informational pamphlet with the approval of the referring clinician/physician (see Appendix L, as well as recruitment brochure).

To further clarify, the investigators will pursue various methods for recruiting subjects, including UTMB or outside physician referrals, outside speech pathologist referrals, referrals from other professionals and community engagement activities. We do not plan a multisite study, but seek the option to widen the scope of patient referrals by contacting other burn centers and burn support groups and through participation in community outreach activities. The physicians will be asked to refer eligible patients; the physicians would not be engaged in the research. Subjects will be seen at their place of residence or UTMB outpatient clinics or via telehealth. Subjects may self-refer from marketing materials. Outreach will include social media, such as postings to burn support group websites or Facebook pages, Speech Pathology special interest group pages, Facebook, UTMB Department of Otolaryngology Facebook page. In all recruitment scenarios, the investigators will notify the subject's managing physician of their participation in the study. If the subject cannot be reached by phone, a letter will mailed to the potential subject with study information.

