Expected benefits include: increasing range of motion for multiple facial muscles and tissues; reducing the impact and appearance of scar tissue; ability to target multiple sites across the face, with particular attention to the cheeks, nasolabial folds, upper lip, mentolabial junction and modiolus; achieving a stretch that currently available tools cannot provide; improved ability to produce different facial expressions; increased speech intelligibility; improved ability to complete oral hygiene.

14. Biostatistics:

Sample size calculation shows that a sample size of 20 (accounting for 10% missing rate) will be able to detect an effect size of 0.7 by using a two-sided paired t-test, if the real study has statistical power of 0.8 and the significance level (alpha) is 0.050.

Descriptive statistics for continuous and categorical variables will be presented as mean \pm SD and quartiles, and frequencies and proportions, respectively. For the weekly measurements, we will use the descriptive statistics and individual trend plots to present the data. The primary outcome is the change in millimeters after the completion of treatment (post – pre measures) for each facial expression. We will use paired t-tests (if data is normally distributed) or non-parametric alternatives (e.g., Wilcoxon signed-rank test) to test if the changes are statistically significant. The change score of facial disability index (FDI) will be analyzed using the same method. The pre-post outcome of the cranial nerve assessment will be classified by categories (Pass-

Pass, Fail-Pass, Fail-Fail), and the frequencies and proportions will be reported. Two-sided statistical significance will be considered for alpha at the 0.05 level for all tests.

References:

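### The Appendix J form dates the final cranial nerve exam at Week 12, but the trial runs 8 weeks and no Week 12 visit is scheduled (minor internal inconsistency)

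*Combined protocol and SAP*

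**What the plan says.** Appendix J has columns for an initial and a final exam, each scored pass or fail, and two completion lines. The first is for Week 1; the second reads "Week #: 12 Completed on". The page carries the same Version 10 footer as the protocol body, and the appendix refers the reader to a separate document for the complete form.

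The body gives a different duration, and gives it consistently:

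- Section 3, Aim 2: "an 8 week active treatment period".
- Section 4: an enrollment screening, "followed by a total of 8 weeks of treatment".
- Section 4, data collection: at the initial assessment and "1 time per week thereafter (+/- 2 days) for the duration of the 8 week trial".
- Section 6: participants using garments, grafting, radiation or other facial surgery "must suspend all of these treatments for the duration of the 2 month trial".
- Section 7 excludes "planned or unplanned surgeries for facial skin grafting around lips or nose or oral commissure release during the upcoming 8 weeks".

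The form feeds the analysis. Sources of Research Material says "We are also collecting data as shown in Appendix H, I, J, K, L", and Section 14 says "The pre-post outcome of the cranial nerve assessment will be classified by categories", with frequencies and proportions to be reported. Section 14 attaches no week to that exam.

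**The concern.** The form that staff would fill in puts the final exam at a time when the rest of the plan has no visit. The week printed on the form is also the only week number given for this exam.

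Two things follow if the form is followed. First, the obligation to suspend other treatments and the surgery exclusion would both have lapsed, so a participant could be back in compression garments or have had surgery without breaking any rule. Any effect of stretching might also have faded. Either could move a participant between the reported categories. Second, the exam would not line up with the facial measurements and the Facial Disability Index taken at the end of treatment, so a Fail-Pass or Fail-Fail result could not be read beside them. If some staff followed the form and others the body text, one small table would mix two time points.

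**Working it through.** The plan gives no calculated figure on this point. Its sample size of 20 does not depend on when this exam is done. The check is therefore a comparison of dates.

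**Inputs.** Treatment length is 8 weeks (Sections 3 and 4). The visit window is +/- 2 days (Section 4). Suspension of other treatments lasts 2 months (Section 6). The form labels are Week 1 and Week 12 (Appendix J). Assumption: treatment starts at the initial exam, which fits the immediate start described under Recruitment Methods and Consenting Process.

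**End of treatment.** 8 x 7 = day 56. With the window, the visit falls on days 54 to 58.

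**Final exam as labelled.** The label can be counted in two ways:

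| Reading of the label | Day of exam | Gap after day 56 |
|---|---|---|
| Week 1 is day 0 | 11 x 7 = 77 | 77 - 56 = 21 days (3 weeks) |
| 12 elapsed weeks | 12 x 7 = 84 | 84 - 56 = 28 days (4 weeks) |

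**Can another reading close the gap?**

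- The visit window cannot: it reaches only day 58.
- Reading 2 months as two calendar months (59 to 62 days) cannot: the smallest remaining gap is 77 - 62 = 15 days and the largest is 84 - 59 = 25 days.
- A delay between the initial exam and first use of the tools would shorten the gap day for day, but it would have to last 3 to 4 weeks to remove it.

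**Would relabelling the line Week 8 be enough?** Not safely. If Week 1 is day 0, Week 8 is 7 x 7 = day 49, which is 56 - 49 = 7 days before treatment ends.

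**Which items could change?** Section 4 lists target muscles that include the buccinator and the zygomaticus major. On the form, puffing the cheeks and smiling with teeth shown plausibly depend on these. Smell, eye movement, gag reflex, jaw jerk and shoulder shrug have no evident route to change from resumed garments or from 3 to 4 weeks without stretching.

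**The case against.** The strongest reply is that this is a stale or mistaken label and nothing more. The body is consistent at 8 weeks or 2 months, weekly visits stop with the trial, and following the form would require a visit that the available protocol does not contain. Section 14 uses pre-post for this exam in the same paragraph that sets the primary outcome after treatment is completed, so an analyst would naturally take the final exam to be at the end of treatment. The form also records the actual completion date, so a late exam could be identified. The complete form, which might carry a different label, is not available.

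Most of this stands. It makes a form error at least as likely as a real off-treatment exam, and it limits the consequence. It does not remove the mismatch: a form used to collect an analysed outcome carries a date that the plan does not support, and Section 14 does not expressly correct it.

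A reader might go further and infer that the trial has an unstated 12-week follow-up, or that the label is left over from a 12-week design. The documents show neither. A reader might also infer that the pre-post results in general are biased. That does not follow: the label is on the cranial nerve form alone, and the primary outcome is separately tied to completion of treatment.

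**Conclusion.** The inconsistency is real and minor. If the form is followed, the post cranial nerve exam falls about 3 to 4 weeks after treatment ends, outside the suspension of other treatments and apart from the other post measures. This rests on treatment starting at the initial exam and on the appendix page matching the form in use.

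The exposure is confined to one descriptive table with no hypothesis test, for an assessment that Section 4 names as neither the primary nor the secondary outcome. Within that table it is mainly the facial items that could shift. The documents do not allow an estimate of how many categories would change, and a shift should not be presumed. Correction is worthwhile because it is nearly free, not because a conclusion of the trial is at risk.

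**What to change.** In Appendix J, and in the separate complete form if it carries the same label, replace the Week 12 line with: *Final exam: end-of-treatment visit (after 8 weeks of treatment, +/- 2 days)*. Avoid a bare Week 8, for the counting reason shown above.

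Add one sentence to Section 14: *The post cranial nerve exam is the one done at the end-of-treatment visit, together with the other post measures.*

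For anyone already examined, use the completion date recorded on the form and list exams outside the window separately from the main table.

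The cost is one label and one sentence. No visit is added, because the exam is placed at the end-of-treatment visit, and no new exam is needed for people who leave early. The downside is that the exam gives no information on whether change lasts after treatment, but the available plan schedules no such assessment anyway. If the investigators do want a Week 12 exam, they should define it as a separate follow-up visit and not use it as the post value.

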5 = No difficulty	2 = Much difficulty
4 = A little difficulty	1 = Usually did not eat because of health
3 = Some difficulty	0 = Usually did not eat because of other reasons

2. How much difficulty did you have drinking from a cup?

Usually did with:

5 = No difficulty	2 = Much difficulty
4 = A little difficulty	1 = Usually did not eat because of health
3 = Some difficulty	0 = Usually did not eat because of other reasons

3. How much difficulty did you have saying specific sounds while speaking?

Usually did with:

5 = No difficulty	2 = Much difficulty, slurring most of speech
4 = A little difficulty	1 = Usually did not eat because of health
3 = Some difficulty	0 = Usually did not eat because of other reasons

4. How much difficulty did you have with your eye tearing excessively or becoming dry?

Usually did with:

5 = No difficulty	2 = Much difficulty
4 = A little difficulty	1 = Usually did not eat because of health
3 = Some difficulty	0 = Usually did not eat because of other reasons

5. How much difficulty did you have with brushing your teeth or rinsing your mouth?

Usually did with:

5 = No difficulty	2 = Much difficulty
4 = A little difficulty	1 = Usually did not eat because of health
3 = Some difficulty	0 = Usually did not eat because of other reasons

(____ - 5) / 5 x 25 = _____ Physical Score

For office use only

(____ - 5) / 5 x 25 = _____ Physical Score Goal

Please Turn
Over for Part 2

Facial Disability Index – Part 2

Please choose the most appropriate response to the following questions related to problems associated with the function of your facial muscles.
For each question, consider your function during the past month.

Office Use Only Score / Goal	Social / Well-being Function
6. _____	6. How much time have you felt calm and peaceful? 6 = All of the time 3 = Some of the time 5 = Most of the time 2 = A little bit of the time 4 = A good bit of the time 1 = None of the time
7. _____	7. How much of the time did you isolate yourself from people around you? 1 = All of the time 4 = Some of the time 2 = Most of the time 5 = A little bit of the time 3 = A good bit of the time 6 = None of the time
8. _____	8. How much of the time did you get irritable toward those around you? 1 = All of the time 4 = Some of the time 2 = Most of the time 5 = A little bit of the time 3 = A good bit of the time 6 = None of the time
9. _____	9. How often did you wake up early or wake up several times during your nighttime sleep? 1 = Every night 4 = Some nights 2 = Most nights 5 = A few nights 3 = A good number of nights 6 = No nights
10. _____	10. How often has your facial function kept you from going out to eat, shop, or participate in family or social activities? 1 = All of the time 4 = Some of the time 2 = Most of the time 5 = A little bit of the time 3 = A good bit of the time 6 = None of the time
Total: _____	For office use only $(\underline{\quad} - 5) / 5 \times 20 = \underline{\quad}$ Social/Wellbeing Score $(\underline{\quad} - 5) / 5 \times 20 = \underline{\quad}$ Social/Wellbeing Score Goal

Physical ( ) + Social ( ) = (  / 200) total FDI Score
Physical ( ) + Social ( ) = (  / 200) total FDI Score Goal
